#### 5.5 DRUG CONCENTRATION MEASUREMENTS AND PHARMACOKINETICS

The plasma concentration and pharmacokinetic analysis of linagliptin will not be performed in this trial.

[REDACTED]

[REDACTED]

Proprietary confidential information.

© 2015 Boehringer Ingelheim International GmbH or one or more of its affiliated companies. All rights reserved.

This document may not - in full or in part - be passed on, reproduced, published or otherwise used without prior written permission.

[REDACTED]

[REDACTED]

[REDACTED]

[REDACTED]

[REDACTED]

[REDACTED]

## 5.7 PHARMACODYNAMICS

No additional pharmacodynamic parameters will be determined in this trial.

[REDACTED]

[REDACTED]

## 6. INVESTIGATIONAL PLAN

### 6.1 VISIT SCHEDULE

All trial visits should be routinely scheduled in the morning, at approximately the same time of day (07:00 AM to 11:00 AM). If a patient mistakenly takes study medication on the morning of a visit before attending the clinic (excluding visits starting before randomisation) or comes in non-fasted where a fasting condition is required (all visits except Screen), the visit should be rescheduled for another day as soon as possible reminding the patient about the expected conditions. The rescheduled visit must take place within the allowed visit window (i.e., in less than 7 days) so that the patient has sufficient study medication.

All patients are to adhere to the visit schedule as specified in the [Flow Chart](#). If any visit has to be rescheduled, subsequent visits should follow the original visit date schedule. The study medication bottles contain sufficient medication to allow for these time windows.

### 6.2 DETAILS OF TRIAL PROCEDURES AT SELECTED VISITS

#### 6.2.1 Screen and Run-In Periods

##### Screen

No trial procedures should begin until the patient has signed the informed consent for the trial.

Patients who have been on stable background therapy [i.e., basal insulin, metformin (optional), and/or alpha-glucosidase inhibitor (optional)] will have the Screen Visit performed.

The Screen Visit does not need to be performed fasting.

After a patient has signed the informed consent, the patient is enrolled in the trial and has begun screening. The patient should be recorded on the enrolment log and be registered in IRT as a screened patient.

Patients who are not eligible due to inclusion and exclusion criteria should be entered as a screen failure in IRT.

##### Run-In

Patients should be fasting (no food or drinks for at least 10 hours, only water is allowed).

Patients will be assigned and receive a placebo kit number through the IRT at this visit.

Patients who fail the Run-In Period following the Visit 2 evaluations should be entered as a screen failure in the IRT.

## 6.2.2 Treatment period

Patients should not take study medication at home on the morning of trial visits during the treatment period.

The treatment period is from Visit 3 to Visit 98. Study medication will be dispensed to patients at each of these visits (except for Visit 98). Patients will be assigned a new medication number through IRT at each visit. Study medication will be administered by the investigator from a new bottle with the IRT-assigned medication number on the day of the visit.

### Treatment Period (Visits 3, 4, 5, 6, 98)

Visits should be performed fasting and as indicated in the [Flow Chart](#), and [Table 4.1.4: 1](#) and the respective protocol sections.

For Visit 98, patients will be entered in IRT as completing or discontinuing treatment.

### Premature discontinuation from the trial (between Visits 3 and 98)

If a patient prematurely discontinues from the 24-week treatment period, the patient must return to the trial site for both Visit 98 and Visit 99 (7 days after Visit 98), which will be performed.

The investigator may initiate any additional antidiabetic therapy based on his or her discretion no sooner than one day after discontinuing study medication.

The scheduled Visit 98 evaluations should be performed for patients who prematurely discontinued from the trial including the following:

- Blood pressure and pulse
- Weight
- Physical examination
- 12-lead ECG
- 
- 
- Collection of blood and urine samples for safety laboratory evaluation
- 
- eDiary
- Diet and exercise counseling

**Proprietary confidential information.**

© 2015 Boehringer Ingelheim International GmbH or one or more of its affiliated companies. All rights reserved.

This document may not - in full or in part - be passed on, reproduced, published or otherwise used without prior written permission.

- Study medication compliance
- Documentation of any adverse events
- Documentation of concomitant therapies

In addition, the patient will be instructed to return in one week for Visit 99 evaluations.

### 6.2.3 End of trial and follow-up period

Visits should be performed as indicated in the Flow Chart and in [Table 4.1.4: 1](#) and the respective protocol sections.

For Visit 99, patients will be entered in IRT as completing or discontinuing the trial.

#### Post-Treatment Period

Patients that complete the trial will take the last dose of study medication the day before Visit 98. The investigator may initiate any additional antidiabetic therapy based on his or her discretion no sooner than one day after Visit 98.

The following Visit 99 evaluations should be performed for all patients returning for this visit including those patients who prematurely discontinued from the trial:

- Blood pressure and pulse
- Collection of blood and urine samples for safety laboratory evaluation
- Return of the HBGM device for assessment of blood glucose levels
- Return of the eDiary
- Documentation of any adverse events
- Documentation of concomitant therapies

The end of the trial is defined as "last patient out", i.e., last visit completed by the last patient.

#### Premature discontinuation from the trial (between Visits 98 and 99)

If a patient discontinues after the 24-week treatment period, the patient should return to the trial site for Visit 99 (the Post-Treatment Visit that occurs 7 days after Visit 98), which will be performed as a trial visit.

The investigator may initiate any additional antidiabetic therapy based on his or her discretion no sooner than one day after discontinuing study medication.

## 7. STATISTICAL METHODS AND DETERMINATION OF SAMPLE SIZE

### 7.1 STATISTICAL DESIGN - MODEL

The objective of the current trial is to investigate the efficacy, safety and tolerability of linagliptin compared to placebo given for 24 weeks as add-on therapy to a stable background of basal insulin, metformin (optional), and/or alpha-glucosidase inhibitors (optional) in elderly patients ( $\geq 60$  years of age) with T2DM and insufficient glycaemic control (i.e., HbA1c of 7.0% to 10%). It is planned to show superiority of linagliptin to placebo for the primary endpoint, the change from baseline in HbA1c (HbA1c after 24 weeks of treatment minus HbA1c at baseline), followed by a decrease in the proportion of patients experiencing at least one confirmed hypoglycaemic event during 24 weeks of treatment, in a hierarchical manner.

HbA1c will be measured in the unit of percent (%) at all clinical visits. A mixed model for repeated measures (MMRM) will be used to compare the change from baseline in HbA1c after 24 weeks of the treatments. The model will include treatment, baseline HbA1c, baseline insulin dose, week, week by baseline HbA1c interaction, and week by treatment interaction.

With regard to efficacy and safety endpoints, the term “baseline” refers to the last observed measurement prior to administration of any randomised study medication.

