### 7.2 NULL AND ALTERNATIVE HYPOTHESES

The superiority of treatment with linagliptin to placebo will be tested for HbA1c change from baseline to Week 24 at the level of  $\alpha=0.05$  (two-sided).

The primary hypothesis can be written as follows:

$H_{0, 1}$ : Mean change from baseline in HbA1c after 24 weeks of treatment with linagliptin  
= Mean change from baseline in HbA1c after 24 weeks of treatment with placebo

$H_{1, 1}$ : Mean change from baseline in HbA1c after 24 weeks of treatment with linagliptin  
 $\neq$  Mean change from baseline in HbA1c after 24 weeks of treatment with placebo

This will be performed on the full analysis set (FAS).

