#### 7.6 DETERMINATION OF SAMPLE SIZE

**This trial will be powered to detect differences between linagliptin and placebo in HbA1c change from baseline after 24 weeks.**

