Description of change		Decrease sample size to 300 (150 per arm) based on the primary endpoint of HbA 1c only, with 100 patients randomized required in Japan. The key secondary endpoint was changed to a secondary endpoint.
Rationale for change		Prescribing practices have changed in the past 5 years and recruitment has proved to be too difficult and slow to achieve the key secondary endpoint sample size requirement.
Section to be changed		Section 1.1
Description of change		An additional sentence was included regarding the rationale for the global protocol amendment.
Rationale for change		As a result of extreme difficulty with recruiting this population, the global protocol amendment expanded the definition of elderly population beginning at age 60.

Proprietary confidential information.

© 2015 Boehringer Ingelheim International GmbH or one or more of its affiliated companies. All rights reserved.

This document may not - in full or in part - be passed on, reproduced, published or otherwise used without prior written permission.

Number of global amendment		1
Section to be changed		Sections 2.2, 3.1, 3.3, and 3.3.2
Description of change		
Decrease of: 1.) age to 60 years old, 2.) lower limit of HbA1c to 7.0% (53 mmol/mol), and 3.) sample size to 300 (150 per arm) based on primary endpoint of HbA1c only, with 100 patients randomized from Japan per regulatory requirements.
 
Section 3.3: A time period ‘of at least 1 year’ has been added to the medical history documentation requirement.
 
Inclusion criterion 2b: The additions of ‘biosimilar’ basal insulin and Humalog Basal® (a suspension of insulin lispro protamine) have been included in order to expand the permitted basal insulins.

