Rationale for change		The original plan was to allow for a 24 hour recall period but was not possible with changes required for the functionality of the eDiary.

Proprietary confidential information.

© 2015 Boehringer Ingelheim International GmbH or one or more of its affiliated companies. All rights reserved.

This document may not - in full or in part - be passed on, reproduced, published or otherwise used without prior written permission.

Number of global amendment		1
Section to be changed		Section 5.3.3 – list number 1
Description of change		The pre-specified analyses will be performed at the end of the trial and the data will be reported separately from the clinical trial report.
Rationale for change		It was subsequently determined that the pre-specified analyses data would be reported separately from the clinical trial report.
Section to be changed		Section 5.3.3.1 – list numbers 1 and 2
		 
		 

Proprietary confidential information.

© 2015 Boehringer Ingelheim International GmbH or one or more of its affiliated companies. All rights reserved.

This document may not - in full or in part - be passed on, reproduced, published or otherwise used without prior written permission.

Number of global amendment	1
Section to be changed	Sections 7.1, 7.2, 7.3, 7.3.1, 7.3.7, 7.4.1, and 7.6
Description of change	
Decrease of age to 60 years old and lower limit of HbA1c to 7.0%. Changing the key secondary endpoint to a secondary endpoint and decreasing sample size to 300 (150 per arm) based on primary endpoint of HbA1c only.
 
[REDACTED]

Rationale for change	
This trial was based on the data of two trials (1218.36 and 1218.63), which used a lower limit in age for one trial and HbA1c in both trials. Prescribing practices have changed in the past 5 years and recruitment has proved to be too difficult and slow to achieve the key secondary endpoint sample size requirement.
 
[REDACTED]

Proprietary confidential information.

© 2015 Boehringer Ingelheim International GmbH or one or more of its affiliated companies. All rights reserved.

This document may not - in full or in part - be passed on, reproduced, published or otherwise used without prior written permission.

**APPROVAL / SIGNATURE PAGE****Document Number: c02204602****Technical Version Number:3.0****Document Name: clinical-trial-protocol**

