5.2 SECONDARY ENDPOINTS

5.2.1 Key secondary endpoints

There are no key secondary endpoints in this trial.

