7.5 SECONDARY ENDPOINTS

7.5.1 Key Secondary Endpoint

Not Applicable.

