10. HISTORY TABLE

Table 10: 1 History table

Version	Date (DD-Mmm-YY)	Author	Sections changed	Brief description of change
Final	12-Oct-16	[REDACTED]	None	This is the final TSAP without any modification
Revised	09-Nov-2016	[REDACTED]	6.2	Table 6.2: 1 additional column defining the type of the IPV, FPG limits adjusted footnote added
			[REDACTED]	[REDACTED]
			6.8	section omitted from TSAP, will move to ADS plan
			7.8.1	age, renal function and background therapy subgroups for AE and hypoglycaemic AE analyses adjusted, [REDACTED]
			[REDACTED]	[REDACTED]

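### The hypoglycaemia secondary endpoint has two event windows, two analysis sets and a probably leftover hierarchical-testing clause, and no readable text reconciles them

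*Protocol*

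**What the plan says.** **Event window.** SAP 6.7 treats measurements as on-treatment up to and including 7 days after study medication stop, and states that this applies to hypoglycaemia both as an efficacy and as a safety endpoint. It adds that visit windows are not applied to hypoglycaemia and that all on-treatment events count. SAP 7.5.2 gives different limits for this analysis: drug stop for patients who discontinue early, the day before drug stop for non-Japanese patients who do not, and day 175 for Japanese patients still on treatment then.

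**Analysis set.** Protocol 7.4.1 says the hypoglycaemia endpoints use the available data of everyone in the TS. SAP 7.5.2 and Table 6.3: 1 use the FAS, which also requires a baseline and at least one on-treatment HbA1c value.

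**Testing status.** Protocol 7.1 plans superiority on HbA1c, followed by a decrease in the proportion of patients "experiencing at least one confirmed hypoglycaemic event during 24 weeks of treatment, in a hierarchical manner". Protocol 7.2 writes one pair of hypotheses, for HbA1c ("The primary hypothesis can be written as follows"). Protocol 7.6 says "This trial will be powered to detect differences between linagliptin and placebo in" HbA1c change. Protocol 5.1.1 lists hypoglycaemia among five secondary endpoints without rank. SAP 5.2.1 says "There are no key secondary endpoints in this trial", and SAP 7.5.1 reads "Not Applicable". SAP section 3 nevertheless says the SAP rests on protocol section 7. The one readable SAP section 4 row on this endpoint re-words it without addressing its status.

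**The concern.** Reducing hypoglycaemia is a stated aim of the trial (protocol 2.2), so its result will be read closely. An analyst following SAP 6.7 and one following SAP 7.5.2 would count different events. One following protocol 7.4.1 and one following the SAP would count different patients. Either choice can change the estimate and, in a close case, which side of 0.05 the p-value falls. Because two rules are written down, the choice should not wait until results are known.

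The hierarchical clause raises a different question. It cannot change the estimate or the p-value. It bears only on whether a hypoglycaemia p<0.05, after a significant HbA1c result, may be presented as a second confirmed claim or as a nominal finding.

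**Working it through.** **1. The plan's own figure.** Protocol 7.6 assumes a difference of 0.77%, SD 1.2%, 150 per arm and a two-sided 5% t-test. The noncentrality is 0.77 / (1.2 × √(2/150)) = 5.56 on 298 degrees of freedom, giving power of 99.98%. This agrees with the stated figure of more than 99%. The readable text gives no planning rate for hypoglycaemia.

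**2. Length of the window difference.** Visit 98 is on day 169 (Flow Chart) and completers take their last dose the day before (protocol 6.2.3), so drug stop is day 168.

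| Patient | SAP 6.7 | SAP 7.5.2 | Difference |
|---|---|---|---|
| Non-Japanese completer | 168 + 7 = day 175 | 168 − 1 = day 167 | 8 days |
| Early discontinuer | stop + 7 | stop | 7 days |
| Japanese, still on treatment | no Week 24 cut given | day 175 | not defined by 6.7 |

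The last row matters for the fix. Japanese patients continue to Week 52 (SAP 6.2 and 7.7), so 6.7 alone cannot limit the endpoint to 24 weeks for them.

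**3. Risk lost by the shorter window.** Assume a constant hazard and risk p by day 175. The loss for a non-Japanese completer is p − [1 − (1 − p)^(167/175)].

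| Assumed risk by day 175 | Loss (percentage points) |
|---|---|
| 20% | 0.82 |
| 30% | 1.15 |
| 40% | 1.42 |
| 50% | 1.61 |

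**4. Effect on significance.** Trials were simulated with 150 per arm, one third Japanese (100 of 300, protocol 3.1), an assumed 10% dropout spread uniformly over time, constant hazard, placebo risks of 20% to 50% and risk ratios of 0.5 to 1.0. Japanese completers were followed to day 175 under both windows. Each simulated trial was analysed both ways with an unadjusted log odds ratio test. The two windows disagreed on p<0.05 in roughly 0.3% to 6.5% of trials, depending on the scenario.

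**5. Analysis set.** The FAS drops treated patients who have no baseline or no on-treatment HbA1c. The documents do not say how many to expect, so no size can be attached.

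**6. Testing status.** If HbA1c is the only confirmatory test, confirmatory error is 0.05. If hypoglycaemia is tested at 0.05 only after HbA1c succeeds, error for the pair is still at most 0.05, because a first false claim requires either a false HbA1c rejection or, if the HbA1c effect is real, a false hypoglycaemia rejection. With HbA1c power near 100% the gate would almost always open, so if the planned HbA1c effect is real the false-positive rate for hypoglycaemia is about 0.050 with or without it.

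**The case against.** **Window.** SAP 7.5.2 is the endpoint-specific rule and SAP 6.7 the general one. SAP 6.1.1 says the residual period depends on the endpoint, and only 7.5.2 supplies a Week 24 cut for Japanese patients. It is natural to let 7.5.2 govern, and the fix does so. But 6.7 is not merely general: it names hypoglycaemia efficacy endpoints expressly, and 6.1.1 sends the reader to 6.7 for the windows. The conflict of wording stands.

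**Set.** The SAP agrees with itself on the FAS. The mismatch is with the protocol, and a redacted row of SAP section 4 may declare the change. That reservation stands.

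**Status.** Almost every readable operative passage treats hypoglycaemia as an ordinary secondary endpoint. The amendment description, cited here only for intent, says "The key secondary endpoint was changed to a secondary endpoint" and lists 7.1 among the sections affected ("Sections 7.1, 7.2, 7.3, 7.3.1, 7.3.7, 7.4.1, and 7.6"). The SAP is later: its first entry, "This is the final TSAP without any modification", is dated October 2016, with a revision in November 2016. The 7.1 clause is probably a leftover, and the statement that the SAP builds on protocol section 7 is weak evidence that it survives. On the other side, naming no key secondary endpoint does not itself rule out a sequence, since an ordinary secondary can be tested second.

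**Stronger readings a reader might infer.** One is that the status of a hypoglycaemia p<0.05 is left open, to be chosen once the result is known. The documents do not support that: the start of protocol 7.3.2 and most SAP section 4 rows cannot be read, so a statement on multiplicity there cannot be excluded. Another is that type I error rises to 1 − 0.95² = 0.0975. That needs both nulls to be true, independent tests and hypoglycaemia claimed as confirmatory without a gate, which neither reading of the plan proposes.

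**Conclusion.** The point holds as a minor inconsistency in how one secondary endpoint is specified. The primary analysis is unaffected.

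- **Window:** high confidence, because both passages are readable and in the same document. The 7 to 8 days follow from the text. The risk loss and the rate of disagreement on significance depend on the assumed risks and constant hazard, and the disagreement rate also on the assumed dropout.
- **Analysis set:** moderate confidence, because the change may be declared in a redacted row. Its effect is not quantifiable from the documents.
- **Hierarchical clause:** moderate confidence, because relevant text is not visible. What is supported is that no readable passage reconciles protocol 7.1 with the rest of the plan. The consequence is one of labelling; no estimate, p-value or confirmatory error rate is harmed.

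**What to change.** Revise the SAP before unblinding:

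1. Add a row to section 4 stating that the Week 24 HbA1c contrast is the only confirmatory test, that the hierarchical wording in protocol 7.1 no longer applies, and that p-values for secondary endpoints are nominal.
2. Make the SAP 7.5.2 window the rule for this endpoint, since it alone defines the Week 24 cut for Japanese patients. Amend the sentence in SAP 6.7 to match, and run the stop + 7 day window as a sensitivity analysis.
3. Use the TS as in protocol 7.4.1. Otherwise, declare the change to the FAS in section 4, if a redacted row does not already do so, and show the TS result alongside.

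The cost is one section 4 row, a sentence or two on window and set, and one or two extra tables. No patients, data or alpha are needed. Correcting protocol 7.1 itself requires the amendment approvals in protocol 8.1, so it can wait for the next amendment, if there is one.

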### 7.2 NULL AND ALTERNATIVE HYPOTHESES

The superiority of treatment with linagliptin to placebo will be tested for HbA1c change from baseline to Week 24 at the level of  $\alpha=0.05$  (two-sided).

The primary hypothesis can be written as follows:

$H_{0, 1}$ : Mean change from baseline in HbA1c after 24 weeks of treatment with linagliptin  
= Mean change from baseline in HbA1c after 24 weeks of treatment with placebo

$H_{1, 1}$ : Mean change from baseline in HbA1c after 24 weeks of treatment with linagliptin  
 $\neq$  Mean change from baseline in HbA1c after 24 weeks of treatment with placebo

This will be performed on the full analysis set (FAS).

### 7.3 PLANNED ANALYSES

The primary analysis will be performed on the FAS. The FAS will consist of all randomised patients who were treated with at least one dose of study medication, had a baseline and at least one on-treatment HbA1c measurement.

The FAS-completers set of patients is defined as all patients in the FAS who complete 24 weeks of treatment and have an HbA1c measurement after 24 weeks of treatment.

**Proprietary confidential information.**

© 2015 Boehringer Ingelheim International GmbH or one or more of its affiliated companies. All rights reserved.

This document may not - in full or in part - be passed on, reproduced, published or otherwise used without prior written permission.

[REDACTED] A protocol violation will be considered important if it can be expected to have a distorting influence on the assessment of the primary endpoint.

Important protocol violations include:

- Randomised study medication: incorrect study medication taken
- Severe violation of treatment compliance
- Severe violation of inclusion criteria
- Non-adherence to other specifications of the protocol that could bias the primary endpoint

Further details will be given in the Trial Statistical Analysis Plan (TSAP).

All patients treated with at least one dose of study medication (the Treated Set) will be included in the safety evaluation.

